9.1.6. Re-treatment Phase

Subjects losing control of disease, defined as PASI score >5 at any visit during Study Parts 2 or 3 (ie, until week 220), will enter the re-treatment arms (groups **2d** or **3c**) with three guselkumab 100 mg administrations starting at that visit (= re-treatment week 0, followed by administration at re-treatment weeks 8 and 16).

If re-treatment is started at a visit, which would usually not require all PROs needed at the re-treatment visit week 0, those PROs will be obtained immediately after efficacy assessments (basis for re-treatment-decision) and prior to drug administration at that visit.

The final efficacy assessment for all subjects in the re-treatment arms will take place 24 weeks after loss of disease control and study termination will be 28 weeks after loss of disease control (final study visit/safety follow-up). At visit week 24 of the re-treatment, the investigator may continue actual treatment with commercially available guselkumab (ie, not provided by the Sponsor) to maintain a q8w interval. Due to the half-life of guselkumab, it is recommended not to start a new therapy during safety follow-up period (ie, 12 weeks after last dose). If the investigator feels strongly that an additional therapy is needed, this should be discussed with the sponsor before initiation of the new therapy.

Subjects with fluctuating disease (ie, PASI score 3 to 5) at the week 68 visit will also get the opportunity to enter the re-treatment-arm (**3c**). The last chance to start re-treatment will be the visit week 220.

9.2. Efficacy Evaluations

Efficacy evaluations chosen for this study are consistent with those utilized to evaluate other therapies for psoriasis. Efficacy evaluations include:

- Psoriasis Area and Severity Index (PASI)
- Nail Assessment in Psoriasis and Psoriatic Arthritis (NAPPA-CLIN)
- Psoriasis-affected Body Surface Area (BSA)
- Dermatology Life Quality Index (DLQI) [PRO]
- Psoriasis Symptom and Sign Diary (PSSD, 7-day version) [PRO]
- Nail associated quality of life and patient- relevant treatment benefit (NAPPA-QoL/-PBI) [PRO]
- Target Lesion Severity Score (TLSS; only for subjects participating in substudies 1 and 2).

9.2.1. Efficacy Assessor Assessments

The efficacy assessor assessments (PASI, NAPPA-CLIN, BSA) will be performed at the site by an efficacy assessor trained by the Sponsor and at the appropriate visits as outlined by the TES.

Efficacy assessments should preferably be done by a dermatologist but if a dermatologist is not available, a health care provider with at least 1 year of experience in performing the efficacy assessments (PASI, NAPPA-CLIN, BSA) may serve as efficacy assessor. Health care providers with less than 1 year of experience may serve as an efficacy assessor based upon the discretion and approval of the Sponsor.

The Sponsor will provide PASI, NAPPA, BSA training prior to the screening of the first subject at each site. If the efficacy assessor was trained by the Sponsor in a previous clinical study within the last 3 years and there is adequate documentation of this training (certification), that training will be considered adequate for this study. However, repeat training prior to start of the study is encouraged. Training documentation of each efficacy assessor should be maintained at the study site. All efficacy assessors at a site must be listed on the delegation log.

9.2.1.1. Psoriasis Area and Severity Index

The PASI is a system used for assessing and grading the severity of psoriatic lesions and their response to therapy ([Feldman, et al. 1996](#)). In the PASI system, the body is divided into four regions: the head, trunk, upper extremities, and lower extremities. Each of these areas is assessed separately for erythema, induration, and scaling, which are each rated on a scale from 0 to 4. The PASI produces a numeric score that can range from 0 (no psoriasis) to 72. A higher score indicates more severe disease.

9.2.1.2. Nail Assessment in Psoriasis and Psoriatic Arthritis

The NAPPA is an instrument for assessing clinical and patient-reported outcomes in nail psoriasis ([Augustin, et al. 2014](#)). It comprises three components:

1. NAPPA-QOL is a 20-item nail-specific quality of life (QoL) questionnaire covering the past week. Signs, stigma and everyday life are rated on a scale from 0 (no suffering) to 4 (high suffering). A global score is computed by averaging all items.
2. NAPPA-PBI is a 24-item questionnaire to assess patient-defined needs before and patient-rated benefits after treatment. The answers are given on a scale from 0 to 4, and a global score is calculated as follows: Each benefit item is multiplied with the respective importance item, and the product is divided by the sum of all importance items. The results are summed up over all items. The resulting global score ranges from 0 (no benefit) to 4 (highest possible benefit).
3. NAPPA-CLIN is an instrument used by the physician to assess the least and the worst involved nail of both hands or both feet with scores ranging from 0 to 16.

9.2.1.3. Psoriasis-affected Body Surface Area

The percentage of the psoriasis-affected body surface area (BSA %) is a system used for assessing the severity of psoriasis ([Ramsay und Lawrence 1991](#)). The plaque coverage is estimated using the rule of palm (1 palm of the hand = 1% BSA).

9.2.1.4. Target Lesion Severity Score

The target lesion severity score (TLSS), also known as target plaque severity score (TPSS), documents the physician's assessment of a subject's target psoriasis lesion according to the following categories: induration, scaling, and erythema. Every effort should be made to ensure that the physician or designee who performed the TLSS evaluations for a subject at randomization performs the TLSS for that subject at all subsequent visits. A description of the TLSS is provided in [Attachment 1](#).

9.2.2. Patient-reported Outcomes

PROs will be assessed in the following order: 1st DLQI, 2nd 7-day version of PSSD, 3rd NAPPA-QoL and 4th NAPPA-PBI). The questionnaires will be completed on paper sheets at the site by subjects at the appropriate visits as outlined by the TES. Data collected on the paper sheets will be handled as source data and will be transferred into the eCRF by the site staff.

9.2.2.1. Dermatology Life Quality Index

The DLQI is a dermatology specific QoL instrument designed to assess the impact of the disease on a patient's QoL. It is a 10-item questionnaire that, in addition to evaluating overall QoL, can be used to assess six different aspects that may affect QoL: 1) symptoms and feelings, 2) daily activities, 3) leisure, 4) work or school performance, 5) personal relationships, and 6) treatment (Finlay und Khan 1994). Each question is scored from 0 to 3, giving a possible score range from 0 (no impact of skin disease on QoL) to 30 (maximum impact on QoL).

9.2.2.2. Psoriasis Symptom and Sign Diary

The PSSD is a questionnaire designed to measure the severity of psoriasis symptoms and signs for the assessment of treatment benefit (Feldmann, et al. 2016). The PSSD is a patient self-administered outcomes instrument that includes 11 items covering symptoms (itch, pain, stinging, burning and skin tightness) and patient observable signs (skin dryness, cracking, scaling, shedding or flaking, redness and bleeding) using 0 to 10 numerical rating scales for severity. Two subscores each ranging from 0 to 100 will be derived: the psoriasis symptom score and the psoriasis sign score. A higher score indicates more severe disease.

A change of ≥ 40 points in PSSD symptom score or sign score, and a ≥ 3 -point change in individual PSSD item scale scores will be defined as clinically meaningful change (response). In this study, the 7-day-version of the PSSD will be used.

9.3. Pharmacokinetics (PK)

Venous blood samples will be collected at the points in time shown in the TES for the determination of serum guselkumab concentrations. Serum collected for PK may additionally be used to evaluate safety or efficacy aspects that address concerns arising during or after the study period. Genetic analyses will not be performed on these serum samples. Subject confidentiality will be maintained.

Each sample will be divided into 2 aliquots (1 aliquot for serum guselkumab concentration and 1 aliquot as back-up sample). Samples must be collected before study drug administration. The exact dates and times of blood sampling must be recorded in the laboratory requisition form. The samples will be shipped to the central lab and analyzed (i) after the completion of Study Part 1 (after week 28 visit) and (ii) after completion of the study including the re-treatment arm for analysis of the respective secondary endpoints.

Subject confidentiality will be maintained. See the Laboratory Manual for further information regarding collection, handling, and shipment of biological samples. The sponsor, or its designee, will assay these samples using a validated, specific, and sensitive immunoassay method under conditions in which the subjects' identity remains blinded.

Note: One additional blood sample for PK assessments will be taken at the time when the subject loses control of disease (PASI score >5 at any visit of Study Parts 2 or 3, or PASI ≥ 3 at week 68). However at R0, PK-samples will only be taken for Study Part 2d (ie, not for Study Part 3c).

9.4. Biomarkers

The samples will be collected according to the points in time specified in the TES. Guidelines and specifications for sample collection and shipment information are provided in the Laboratory Manual.

Immunophenotyping of PBMCs

Whole blood samples will be collected from subjects who are enrolled by the sites selected for substudy 1. Measurements include the quantity of different PBMCs. Immunophenotyping of PBMCs will be performed using flow cytometry by sites with expertise to conduct FACS-based cellular immunophenotypic characterization of freshly isolated blood cells. Subjects' identity will remain blinded.

Immunophenotyping of skin biopsies

6 mm biopsies will be collected from subjects who are enrolled by the sites selected for substudy 1. Measurements include the quantity of Th17, Tc17 non-TRM T cells, TRM T cells, Tregs and antigen presenting cells. Immunophenotyping of skin biopsies will be performed using flow cytometry by sites with expertise to conduct FACS-based cellular immunophenotypic characterization of freshly isolated biopsies. Subjects' identity will remain blinded.

Gene expression analysis of skin biopsies

Skin biopsy samples will be collected according to the Time and Events Schedule from a subset of subjects who consent to participate in substudy 2. Each 6 mm biopsy will be split in two parts; one part will be stored for RNA gene expression analysis, while the other part will be frozen in OCT and stored for H&E, IHC and IF analyses. If two 3 mm biopsies have been taken instead of the 6 mm biopsy, one 3 mm biopsy will be stored in RNAlater for RNA preparation and gene expression analysis, while the other 3 mm biopsy will be frozen in OCT and stored for H&E, IHC and IF analyses.

The samples will be shipped to the central lab and analyzed later under conditions in which the subjects' identity remains blinded.

Serum biomarkers

Serum samples of approximately 8.5 mL will be collected from all subjects to assess PD markers associated with the response to guselkumab as well as markers related to psoriasis (**substudy 3**). Measurements will include but are not limited to serum IL-17A, IL-17F, IL-22 levels and beta defensin. Detection and characterization of cytokines will be done using various immune assays.

9.5. Pharmacogenomic (DNA) Evaluations

At week 0, a single whole blood sample of approximately 6 mL will be collected from a subset of subjects who consent to participate in substudy 4. The goal of the pharmacogenomic (DNA) analysis is to search for genetic factors that may influence molecular effects, clinical efficacy, or tolerability of guselkumab and to identify genetic factors associated with psoriasis. They will be performed using validated assay methods by or under the supervision of the Sponsor.

DNA samples will be used for research related to guselkumab. They may also be used to develop tests/assays related to guselkumab. Pharmacogenomic research may consist of the analysis of one or more candidate genes or of the analysis of genetic markers throughout the genome in relation to guselkumab.

9.6. Safety Evaluations

Safety and tolerability of guselkumab will be monitored until 12 weeks after last administration of study drug by collecting information on AEs, including injection site and allergic reactions, clinical laboratory tests (hematology, chemistry and pregnancy testing), physical examinations, vital signs, concomitant medication review, and early detection of tuberculosis (TB), as specified in the TES. Subjects participating in Study Part 3 and not treated in the re-treatment arm will be monitored through week 220 by collecting information on AEs, including injection site and allergic reactions, vital signs, weight, and concomitant medication review. Any clinically significant abnormalities persisting at the end of the study/early withdrawal will be followed by the investigator until resolution or until a clinically stable endpoint is reached.

In cases of self-administration of SC study intervention at home, subjects are requested to contact their treating physician as soon as possible to consider reporting of an adverse event.

Clinical laboratory safety monitoring may be performed at a certified local laboratory identified by the study site rather than at the central laboratory; for selected measures (eg, urine pregnancy), home testing may be employed.

The study will include the following safety evaluations:

Adverse Events

AEs will be reported by the subject for the duration of the study. AEs will be followed by the investigator as specified in Section 12.

Injection Site Reactions

An injection site reaction (ISR) is any unfavorable or unintended sign that occurs at the study drug injection site. After administration of study drug at week 0, all subjects will be carefully observed at the study site for at least 30 minutes after the SC injection of study drug for symptoms of an ISR. If an ISR is observed, the subject should be treated at the investigator's discretion. Any adverse reaction (eg, pain, erythema, induration) should be noted on the AE page of the eCRF.

Allergic Reactions

Subjects must be observed carefully for symptoms of an allergic reaction (e.g., rash, urticaria, itching, shortness of breath, or drop in blood pressure) for at least 30 minutes after the study drug injection. If an allergic reaction is observed, treatment should be administered according to standard practice. Any allergic reaction should be noted on the AE page of the eCRF.

Clinical Laboratory Tests

Blood samples for hematology, serum chemistry and serology will be collected. The investigator must review the results, document this review, and record any clinically relevant changes occurring during the study in the AE section of the CRF. Clinically significant abnormal laboratory values should be followed as clinically appropriate or until they return to normal or are otherwise explained by the investigator. Laboratory reports must be filed with the source documents.

The following tests will be performed by the central laboratory:

- **Hematology Panel:**
 - hemoglobin
 - hematocrit
 - red blood cell (RBC) count
 - platelet count
 - white blood cell (WBC) count
 - lymphocytes (%, absolute)*
 - monocytes (%, absolute)*
 - neutrophils (%, absolute)*
 - eosinophils (%, absolute)*
 - basophils (%, absolute)*
- **Serum Chemistry Panel:**
 - sodium
 - potassium
 - chloride
 - blood urea nitrogen (BUN)
 - creatinine
 - glucose
 - aspartate aminotransferase (AST)
 - alanine aminotransferase (ALT)
 - gamma-glutamyltransferase (GGT)
 - total bilirubin
 - magnesium
 - alkaline phosphatase (AP)
 - creatine phosphokinase (CPK)
 - lactic acid dehydrogenase (LDH)
 - uric acid
 - calcium
 - phosphate
 - albumin
 - total protein
 - cholesterol
 - triglycerides
- **Serology:** Samples for HIV antibody, hepatitis B (see [Attachment 3](#)) and hepatitis C virus antibodies will be obtained at screening.
- **Urine Pregnancy Testing** for women of childbearing potential will be done at screening and at the times shown in the TES. Pregnancy tests must be completed and negative at the study visit prior to administration of study drug. All pregnancy test results must be recorded in study source documents.

Vital Signs

Blood pressure and heart rate measurements will be assessed as specified in the TES. If any clinically significant changes in vital signs are noted, they must be reported as AEs and followed to resolution, or until reaching a clinically stable endpoint.

Physical Examination

Physical examinations will be performed by body systems, eg, eyes, ears/nose/throat, head/neck/thyroid, heart, lung, chest, abdomen etc., by the investigator or designated physician, nurse practitioner or physician assistant as specified in the TES. Total body skin examination will be performed to determine the presence of any suspected malignant skin lesions including basal cell carcinoma, squamous cell carcinoma, and melanoma. In addition, the study agent injection site is to be evaluated. Any new, clinically significant finding must be captured as an AE. In addition, resolution of any abnormal findings during the study will be noted in the source document and in the eCRF.

Body height and weight

Body height and weight will be measured as specified in the TES. Subjects will be instructed to remove shoes and outdoor apparel and gear prior to these measurements.

Concomitant Medication Review

Concomitant medications will be reviewed and reported at each visit. A list of restricted and prohibited concomitant medications is provided in Section 8.

Early Detection of Active Tuberculosis

To aid in the early detection of TB reactivation or new TB infection during study participation, subjects must be evaluated for signs and symptoms of active TB at scheduled visits. The following series of questions is suggested for use during the evaluation:

- "Have you had a new cough of >14 days' duration or a change in a chronic cough?"
- "Have you had any of the following symptoms:
 - Persistent fever?
 - Unintentional weight loss?
 - Night sweats?"
- "Have you had close contact with an individual with active TB?" (If there is uncertainty as to whether a contact should be considered "close," a physician specializing in TB should be consulted.)

If the evaluation raises suspicion that a subject may have TB reactivation or new TB infection, an immediate and thorough investigation should be undertaken, including, where possible, consultation with a physician specializing in TB.

Investigators should be aware that TB reactivation in immunocompromised subjects may present as disseminated disease or with extrapulmonary features. Subjects with evidence of active TB should be referred for appropriate treatment.

Subjects who experience close contact with an individual with active TB during the conduct of the study must have a repeat chest radiograph, a repeat QuantiFERON-TB Gold test (a repeat tuberculin skin test in countries in which the QuantiFERON-TB Gold test is not approved/registered or the tuberculin skin test is mandated by local health authorities) and, if possible, referral to a physician specializing in TB to determine the subject's risk of developing active TB and whether treatment for latent TB is warranted.

Study drug administration should be interrupted during the investigation. A positive QuantiFERON-TB Gold test result should be considered detection of latent TB. If the QuantiFERON-TB Gold test result is indeterminate, the test should be repeated. The QuantiFERON-TB Gold test will generally be performed by the central laboratory. However, if available, test results from local laboratory can be accepted.

If recommended, treatment for latent TB must be initiated prior to or simultaneously with the administration of further study agent. Subjects who discontinue treatment for latent TB prematurely or who are noncompliant with therapy must immediately discontinue further administration of study drug and be encouraged to return for all subsequent scheduled study visits according to the TES.

9.7. Sample Collection and Handling

Actual dates and times of sample collection must be recorded in the CRF or laboratory requisition form. Refer to the TES for the timing and frequency of all sample collections.

Instructions for the collection, handling, storage, and shipment of samples are found in the laboratory manual that will be provided. Collection, handling, storage, and shipment of samples must be under the specified, and where applicable, controlled temperature conditions as indicated in the laboratory manual.

10. SUBJECT COMPLETION/DISCONTINUATION OF STUDY TREATMENT/ WITHDRAWAL FROM THE STUDY

10.1. Completion

A subject will be considered to have completed Study Part 1 if he or she has completed assessments at the week 28 visit. A subject will be considered to have completed Study Part 2 if he or she has completed the assessments of week 68. A subject will be considered to have completed Study Part 3 if he or she has completed assessments at week 220 or re-treatment (week 24/28 SFU). Subjects entering the re-treatment arms (2d or 3c) will be considered to have completed the re-treatment arm if he or she has completed assessments at week 24 visit after start of re-treatment.

10.2. Discontinuation of Study Treatment

A subject will not be automatically withdrawn from the study if he or she has to discontinue treatment before the end of the treatment regimen.

A subject's study treatment must be permanently discontinued if:

- The investigator believes that for safety reasons or tolerability reasons (eg, AE) it is in the best interest of the subject to discontinue study treatment.
- The subject shows no response to study treatment at week 28, defined as no change or worsening of PASI score at week 28 in comparison to week 0.
- The subject becomes pregnant.
- The subject is diagnosed with a malignancy, with the exception of no more than 2 localized basal cell skin cancers that are treated with no evidence of recurrence or residual disease.
- The subject is deemed ineligible according to the following TB screening criteria:
 - A diagnosis of active TB is made.
 - A subject has symptoms suggestive of active TB based on follow-up assessment questions and/or physical examination or has had recent close contact with a person with active TB and cannot or will not continue to undergo additional evaluation.
 - A subject undergoing evaluation has a chest radiograph with evidence of current active TB and/or a positive QuantiFERON-TB Gold test result and/or an indeterminate QuantiFERON-TB Gold test result on repeat testing (refer to Section [9.6](#)) (and/or a positive tuberculin skin test result in countries in which the QuantiFERON-TB Gold test is not approved/registered or the tuberculin skin test is mandated by local health authorities). Indeterminate QuantiFERON-TB Gold test results should be handled as described in Section [9.6](#).

- A subject receiving treatment for latent TB discontinues this treatment prematurely or is noncompliant with the therapy.
- A subject receiving treatment for latent TB discontinues this treatment prematurely or is noncompliant with the therapy.
- The subject initiates a protocol-prohibited medication, eg, for a worsening of his or her psoriasis (unless agreed to by the medical monitor).
- The subject withdraws consent for administration of study drug.
- The subject is unable to adhere to the study visit schedule or comply with protocol requirements.
- The subject develops an allergic reaction such as bronchospasm with wheezing and/or dyspnea requiring ventilatory support, or symptomatic hypotension that occurs following a study drug administration.
- The subject has a reaction resulting in myalgia and/or arthralgia with fever and/or rash (suggestive of serum sickness and not representative of signs and symptoms of other recognized clinical syndromes) occurring 1 to 14 days after an injection of study drug. These may be accompanied by other events including pruritus, facial, hand, or lip edema, dysphagia, urticaria, sore throat, and/or headache.
- Discontinuation of study treatment should be considered for subjects who develop a serious or opportunistic infection. Discussion of such subjects with the medical monitor or designee should also be considered.
- Discontinuation of study treatment for abnormal liver tests is required by the investigator when a subject meets one of the conditions outlined in [Attachment 8A](#) or in the presence of abnormal liver chemistries not meeting protocol-specified stopping rules if the investigator believes that it is in best interest of the subject.

Refer to [Attachment 8B](#) for follow-up assessments (and study treatment restart guidelines) following abnormal liver test results. Study Sponsor must provide written approval before study intervention is restarted.

Subjects who decide to discontinue study drug administration must be interviewed by the investigator to determine if a specific reason for discontinuing study drug can be identified. Subjects should be explicitly asked about the possible contribution of AEs to their decision to discontinue study drug; investigators should confirm that any AE information elicited has been documented. If a subject elects to discontinue study drug due to an AE, the event should be recorded as the reason for study drug discontinuation, even if the investigator's assessment is that the AE would not require study drug discontinuation. The reason for study drug discontinuation must be documented in the eCRF and in source documents. Study drug assigned to a subject who discontinues may not be assigned to another subject.

If a subject discontinues study treatment for any reason before his or her last scheduled injection, he or she should return for the remaining regularly scheduled study visits for at least 12 weeks after receiving the last administration of study drug.

Withdrawal From the Study

A subject will be withdrawn from the study for any of the following reasons:

- Lost to follow-up
- Withdrawal of consent
- Death.

To ensure access for subject follow-up, study sites should try to obtain both primary and secondary telephone contact numbers from subjects (eg, home, work, and mobile phones), as well as other contact information such as email addresses, and emphasize the importance of follow-up information to the subject at study start.

If a subject is lost to follow-up, every reasonable effort must be made by the study site personnel to contact the subject and determine the reason for discontinuation/withdrawal. The measures taken to follow up must be documented.

Withdrawal of consent should be a very unusual occurrence in a clinical trial; the investigator should make every effort to maintain good subject relationships to avoid withdrawals of consent. For subjects who truly request withdrawal of consent, it is recommended that the subject withdraw consent in writing; if the subject or the subject's representative refuses to do so or is physically unavailable, the study site should document the reason for the subject's failure to withdraw consent in writing, sign the documentation, and maintain it with the subject's source records.

When a subject withdraws before completing the study, the reason for withdrawal is to be documented in the CRF and in the source document. Study drug assigned to the withdrawn subject may not be assigned to another subject. Subjects who withdraw will not be replaced. If a subject withdraws from the study before the end of week 68 early termination visit (ETV) assessments should be obtained. If the reason for withdrawal from the study is withdrawal of consent then no additional assessments are allowed.

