- a. Have no history of latent or active TB before screening.
 - o an exception is made for subjects who have a history of latent TB and
 - are currently receiving treatment for latent TB,
 - will initiate treatment for latent TB before the first administration of study drug,
 - or have documentation of having completed appropriate treatment for latent TB within 5 years before the first administration of study drug.
- Note:** It is the responsibility of the investigator to verify the adequacy of previous anti-TB treatment and to provide appropriate documentation.
- b. Have no signs or symptoms suggestive of active TB upon medical history and/or physical examination.
- c. Have had no recent close contact with a person with active TB or, if there has been such contact, will be referred to a physician specializing in TB to undergo additional evaluation and, if warranted, receive appropriate treatment for latent TB before the first administration of study drug.
- d. Within 2 months before baseline, have a negative QuantiFERON®-TB Gold test result, or have a newly identified positive QuantiFERON-TB Gold test result) in which active TB has been ruled out and for which appropriate treatment for latent TB has been initiated before baseline. Within 2 months before baseline, a negative tuberculin skin test, or a newly identified positive tuberculin skin test in which active TB has been ruled out and for which appropriate treatment for latent TB has been initiated before baseline, is additionally required if the QuantiFERON-TB Gold test is not approved/registered in that country or the tuberculin skin test is mandated by local health authorities.

Note: The QuantiFERON-TB Gold test and the tuberculin skin test are not required at baseline for subjects with a history of latent TB and ongoing treatment for latent TB or documentation of having completed adequate treatment as described above; subjects with a documentation of having completed adequate treatment as described above are not required to initiate additional treatment for latent TB.

- e. Have a chest radiograph (posterior-anterior and lateral views, or per country regulations where applicable), taken within 3 months before the first administration of study drug and read by a qualified radiologist, with no evidence of current, active TB or old, inactive TB.
11. Agrees not to receive a live virus or live bacterial vaccination during the study, or within 3 months after the last administration of study drug.

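### Protocol Sections 10.2 and 9.6 give different consequences for a positive QuantiFERON test during the study when active TB is not found: permanent discontinuation in one, interruption with conditional further dosing in the other

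*Protocol*

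**What the plan says.** Protocol Section 10.2 introduces its list with "A subject's study treatment must be permanently discontinued if". One entry is headed "The subject is deemed ineligible according to the following TB screening criteria". Beneath it is a subject undergoing evaluation whose chest radiograph shows current active TB "and/or a positive QuantiFERON-TB Gold test result and/or an indeterminate QuantiFERON-TB Gold test result on repeat testing". A diagnosis of active TB is a separate item in the same list. The entry then adds "Indeterminate QuantiFERON-TB Gold test results should be handled as described in Section" 9.6.

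Protocol Section 9.6, under early detection of active TB, says that subjects with close contact during the study "must have a repeat chest radiograph, a repeat QuantiFERON-TB Gold test" and, if possible, referral to a TB specialist. Study drug is interrupted while this is investigated. The section continues: "A positive QuantiFERON-TB Gold test result should be considered detection of latent TB", and then "If recommended, treatment for latent TB must be initiated prior to or simultaneously with the administration of further study agent". Its immediate stop is for subjects who end latent-TB treatment early or do not comply with it.

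Protocol Section 4.1, criterion 10, admits subjects with a history of latent TB who are on treatment, will start it before first dose, or "have documentation of having completed appropriate treatment for latent TB within 5 years before the first administration of study drug". Those with ongoing or documented completed treatment need no QuantiFERON test at baseline.

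**The concern.** A site with a positive test in an exposed subject, active TB ruled out and latent-TB treatment started, finds a mandatory permanent stop in one section. In the other it finds a path that can lead back to dosing. Two sites could treat the same finding differently and each cite the protocol.

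The difficulty is plainest for a subject enrolled with treated latent TB. That subject may enter without a QuantiFERON test, but Section 9.6 states no exemption from repeat testing after close contact. If the test is positive, Section 10.2 read literally ends treatment for a status that was accepted at entry.

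The choice also reaches the analysis. Protocol Section 11.11 counts a subject who discontinues study treatment before week 68 as a non-responder for the primary endpoint. A subject kept on treatment under Section 9.6 is judged on the week 68 PASI.

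**Working it through.** The check is mainly textual. Take one case: a subject in Study Part 2 has close contact with active TB, the repeat QuantiFERON is positive, active TB is not diagnosed, and latent-TB treatment is recommended and taken.

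| Question | Section 10.2 | Section 9.6 |
|---|---|---|
| Does it cover the case? | Yes: subject undergoing evaluation | Yes: subject investigated after close contact |
| What does the positive test mean? | TB ineligibility | Latent TB |
| Effect on dosing | Mandatory permanent discontinuation | Interruption, then possible further dosing |
| What forces a stop? | The positive test alone, among other items | Stopping or not complying with latent-TB treatment |

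1. *Is the positive test sufficient alone in 10.2?* Yes. It is joined to the radiograph item by and/or. Because a diagnosis of active TB is listed separately, the test result is an additional trigger.
2. *Does the heading about screening criteria reconcile them?* No. At screening (Sections 4.1 and 9.1.2.1) a newly positive test does not exclude a subject once active TB is ruled out and latent-TB treatment is started.
3. *Does the reference to 9.6 reconcile them?* Not clearly. A parenthetical reference stands at the end of the radiograph, positive and indeterminate items, and could attach to all of them or only the last. The sentence that says how to handle results names indeterminate ones only.
4. *Does the separate 10.2 item on abandoned latent-TB treatment help?* It shows that some subjects on such treatment are expected to receive study drug. They may have been treated since screening, so it supports the conflict without proving it.

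*Size per subject.* Section 4.3 of the Overall Safety SAP gives 148 subjects randomised to q8w and 149 to q16w. One subject moved from responder to non-responder changes the arm's rate by:

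- q8w: 1/148 = 0.68 percentage points
- q16w: 1/149 = 0.67 percentage points

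Both are about 0.7 points, against a non-inferiority margin of 10 points. The documents give no number of on-study TB contacts or positive tests, so a total effect cannot be computed.

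**The case against.** The strongest reply is that Section 9.6 never orders dosing to resume. Its sentence on further study agent begins with a condition and fixes only when latent-TB treatment must start relative to any later dose. That is right: the conflict is between a mandatory stop and a conditional, implied continuation. It remains a conflict, because a rule about further dosing after a positive test has little purpose if the positive test has already ended dosing.

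A second reply is that the parenthetical in 10.2 sends the whole list to 9.6; otherwise the later sentence on indeterminate results would be redundant. This is a fair reading, so it cannot be said that 10.2 defers to 9.6 for indeterminate results only. But the ambiguity does not remove the problem. If positives are also referred to 9.6, the reader arrives at a different outcome from the one that 10.2 mandates.

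Third, both sections are protective: 9.6 interrupts dosing during the investigation and 10.2 stops it if active TB is diagnosed. This stands and limits the gap to a positive test without active TB.

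Fourth, a reader might infer that the per-protocol set is affected, because failing to withdraw a subject who met withdrawal criteria is a listed major deviation. That list is in Appendix 4 of the Re-treatment and Part 3 SAPs, and both state that no per-protocol analysis will be done. The Part 2 SAP is not among the documents. The inference is not supported.

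**Conclusion.** The contradiction is real and confined to a positive QuantiFERON result during the study without active TB. Sections 9.6 and 10.2 must be reconciled. Nothing here says which consequence is clinically right.

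The reading applied can change an individual's primary-endpoint status, by about 0.7 percentage points of an arm's responder rate per subject. This assumes that the subject would have had PASI below 3 at week 68 if continued.

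A reader might go further and infer that the non-inferiority result is compromised. The documents do not support that. They give no frequency, treatment was double-blind with 1:1 allocation, and nothing suggests that TB exposure or the section followed differed by arm. A shift in the treatment difference needs such an imbalance. Nor should the 880 subjects treated in Part 1, the 525 in group 2c and the 236 re-treated be added up as the population exposed to the conflict. These groups overlap: the 525 come from the 880, and the 236 from the 297 randomised, who are also among the 880.

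The point therefore rests mainly on having one reading of a TB safety rule.

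**What to change.** - Reconcile Sections 9.6 and 10.2 so that a positive test without active TB has one stated consequence, including for subjects enrolled with completed or ongoing treatment for latent TB. The sponsor's medical team decides which rule applies.
- Make the cross-reference in 10.2 cover positive as well as indeterminate results.
- The SAP introductions report the confirmatory Part 2 analysis as already done, so new wording cannot alter how those subjects were handled. List any on-study positive QuantiFERON results, with the action taken and the week 68 classification, and check that like cases were handled and classified alike.

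The cost is a wording change in two sections, a site memo if any dosing remains, and one data listing. No new procedure or assessment is needed.
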